2.2 Secondary Objectives

2.2.1 Secondary Objective 1: Treatment Outcome

- SO1a: To determine the difference in unbeneficial treatment between FDG-PET/CT driven and routine surgery in this population including thyroid lesions of all sizes (i.e. both ≤10 mm and >10mm).
- SO1b: To determine the effect of incorporation of FDG-PET/CT on the complication-ratio.
- SO1c: To determine the false-negative rate of FDG-PET/CT in this population (i.e. in how many patients with malignancy will watchful-waiting be performed) based on both 12-month and (retrospective) 5-year follow-up.
- SO1d: To determine the influence of lesion size, pathological classification and patient characteristics on the diagnostic accuracy (subgroup analysis) of FDG-PET/CT.
- SO1e: To determine whether incorporation of FDG-PET/CT of the head and neck leads to overdiagnosis in non-thyroidal incidental findings (whole-group analysis).
- SO1f: To determine the short-term overall and disease free survival in both study arms.
- SO1g: To determine which factors hamper implementation of this modality for this indication (structured interviews).
- SO1h: To determine the fraction of patients that cannot be reassured by a negative PETscan (experimental arm only) despite careful selection of patients (implementability).

2.2.2 Secondary Objective 2: Reported Health Related Quality of Life

- SO2a: To determine the impact on the experienced HRQoL between the group with and without FDG-PET/CT according to 4 different questionnaires at 4 timepoints during the first 12 months after FDG-PET/CT.
- SO2b: To determine whether patients in the experimental arm with negative PET-findings have a different HRQoL than those who receive surgery independent of the FDG-PET/CT results.

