Rationale: Only about ¹/₄ of patients with thyroid nodules with indeterminate cytology are proven to suffer from a malignancy at diagnostic hemithyroidectomy. Therefore $\sim \frac{3}{4}$ is operated upon unbeneficially. Recent studies using FDG-PET/CT have suggested that it can decrease the fraction of unbeneficial procedures from ~73% to ~40%. Thereby the direct costs per patient, the number of hospitalization and average sick leave days might decrease and the experienced HRQoL might increase. A study will be undertaken to show the additional value of FDG-PET/CT after indeterminate cytology with respect to unbeneficial procedures, costs and utilities. Main objective: To determine the impact of FDG-PET/CT on decreasing the fraction of patients with cytologically indeterminate thyroid nodules undergoing unbeneficial patient management. Study design: A prospective, multicentre, randomised, stratified controlled blinded trial with an experimental study-arm (FDG-PET/CT-driven) and a control study-arm (diagnostic hemithyroidectomy, independent of FDG-PET/CT-result). Study **population:** Adult patients with a cytologically indeterminate thyroid nodule, without exclusion criteria, in 15 (university and regional) hospitals distributed over the Netherlands. Intervention: One single FDG-PET/low-dose non-contrast enhanced CT of the head and neck is performed in all patients. Patient management depends on allocation and results of this FDG-PET/CT. Main study parameters/endpoints: The number of unbeneficial interventions, i.e. surgery for benign disease or watchful-waiting for malignancy. For secondary objectives: complication rate, consequences of incidental PET-findings, number of hospitalisation and sick leave days, volumes of healthcare consumed, experienced HRQoL, genetic, cytological and (immuno)histopathological features of the nodules. Sample size calculation/data analysis: Based on above-mentioned estimated reduction in unbeneficial interventions from ~73% to ~40%, at least 90 patients with nodules>10 mm need to be analysed (2:1 allocation, α =0.05, power=0.90, one-tailed Fisher's exact test). After correction for nodule size and data-attrition, 132 patients need to be included in total. Intention-to-treat analysis will be performed. Incremental Net Monetary Benefit based on the total direct costs per patient and the gain in HRQoL-adjusted survival years are computed. Cytological, histological and genetic parameters and their correlation to FDG-avidity will be described. Nature and extent of the burden and risks associated with participation, benefit and group relatedness: All patients undergo one FDG-PET/CT scan of head/neck (effective dose: <3.5 mSv) and are asked to fill in 6 questionnaires at 4 time points. FDG-PET/CT negative patients in the experimental arm will undergo a single confirmatory US (±FNAC). An interim/posterior analysis of the control subjects is performed to ensure oncological safety. In case of an unexpected high false-negative ratio in this control arm, all patients will be advised to undergo surgery.

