1.3 Role of FDG-PET/CT in FNAC-indeterminate thyroid nodules

In 2006, our group published a prospective study on the results of FDG-PET in 44 patients with FNAC-indeterminate thyroid nodules. We described a positive and negative predictive value for malignancy of 32% and 100%, respectively (prevalence: 14%) [10]. As our findings were supported by several other studies [11-15], all with similar negative predictive values but

varying positive predictive values, we performed a systematic review and meta-analysis of the literature [4]. The prevalence of benign disease, histologically determined in all these patients after resection, was 74%. In all these patients, FDG-PET/CT was performed prior to surgery on previous generation PET/CT-scanners. Only 3 out of 83 patients with a negative FDG-PET and 55 out of 142 patients with a positive scan showed a malignancy at diagnostic surgery (negative and positive predictive value: 96% and 39%, respectively. The sensitivity of FDG-PET/CT was strongly related to the size of the TN, due to limited spatial resolution of the PET(/CT) scanners used. Due to the limited specificity of the FDG-PET/CT for malignancy, the positive predictive value was found to be poor (Appendix IV: Performance of FDG-PET/CT in indeterminate thyroid nodules, §15.4, p92). Very recently, these data were confirmed by a prospective series of 46 patents with FNAC (non-oncocytic) follicular lesions (Bethesda category III and IV) larger than 20 mm (DTC prevalence: 28%) with a negative and positive predictive value of 61% and 94%, respectively [16]. The authors state that FDG-PET/CT could reduce the number of diagnostic (hemi)thyroidectomies by 13-25%.

Based on the high sensitivity of FDG-PET/CT to detect malignancy in FNAC-indeterminate thyroid nodules, we postulate that incorporation of this imaging modality in the diagnostic workup of these nodules could decrease the prevalence of benign nodules at the time of diagnostic hemithyroidectomy from 74% to 39%. Due to the limited specificity of FDG-PET/CT, still 61% of operated patients will be diagnosed with a benign disorder (i.e. patients with false-positive FDG-PET/CT), being 74% prior to the inclusion of FDG-PET. Although this seems a moderate improvement, the number of hemithyroidectomies for FNAC-indeterminate nodules is reduced by 37%. We therefore consider this modality potentially valuable tool in this category of patients.

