3. STUDY DESIGN

A partially-blinded, prospective, multi-centre, block-randomised controlled trial (RCT) is designed. After obtaining written informed consent, patients are registered centrally, FNAC is reviewed centrally and thereafter patients are randomised to either the experimental study-arm (arm A: FDG-PET/CT driven management decisions) or a control study-arm (arm B: surgery regardless FDG-PET/CT result) using a 2:1 allocation ratio. The latter is performed both for methodological purposes (the treatment of the subjects in the control study arm is well investigated and described before) and to satisfy the assumption that patient prefer the experimental study-arm. The result of randomization is blinded to the treating physicians and central FDG-PET/CT review committee. Allocation is adaptively stratified using the minimisation method on the centre of inclusion and the most prognostic features of DTC known at this stage of patient work-up: (US) lesion size (0-10 mm/11-20 mm/21-40 mm/40+ mm), patient sex, patient age (<45yr, \geq 45yr) and Bethesda classification according to central review committee (atypia of unknown significance/follicular lesion of unknown significance (III) or (suspicion) for a follicular neoplasia (IV)).

Based on the study arm allocation and PET result, treating physicians will either be told to cancel scheduled diagnostic thyroid surgery (allocation to the experimental arm with a negative FDG-PET/CT at central review or ~32/132 patients) or to proceed with surgery (all other cases or 100/132 patients). In case surgery is cancelled the patients need to be followed-up by watchful waiting and a confirmatory ultrasonography (including FNAC) after 12 months. Patient allocation will not be disclosed to prevent study withdrawal, however in case surgery is cancelled unblinding is unavoidable (~25% of all included patients).

The Gold Standard is histology, revised by a (central) dedicated pathologist panel, obtained from surgery or 12-months follow-up, including US (+FNAC). All patients will be followed for at least 12 months after FDG-PET/CT to ensure all direct costs and complications are noted. Five years after inclusion of the last patient, long-term follow-up will be determined based on patient file review and contact with the general practitioner (flowchart Figure 1, p34 and

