4.4 Sample size calculation

Based on the main objective, it is expected that FDG-PET/CT can reduce unjust treatment from ~73.1% (=136/186 benign lesions >10mm) to ~40.3% (=75/186 false-positive and false-negative lesions >10mm, §1.3, p19). Using G*Power version 3.1.9.2. (and validated using JMP from SAS version 9.0.1, STATA version 12.0SE and PASS version 2011), we computed using an α error probability of 0.025 (=0.05/2, Bonferroni correction for interim analysis) a power of 0.80 and an allocation ratio of N_A:N_B=2:1, we need to include at least 90 patients in total (one-tailed test) to establish this difference (60+30 patients in arm A and B respectively).

Since around 82.7% (=186/225, §1.3, p19) fulfil the size criterion, at least 111 patients (74+37 patients in arm A and B respectively) need to be included. Accounting for additional 15% data loss at the final end-point, 132 patients should be included (88+44 patients in arm A and B respectively) (Figure 2, p40).

This total number of patients could at best (assuming no data loss) discern a reduction of 26.6% unjust treatment in the whole population with an actual α error probability of 0.016 and a power of 0.80. This is based on a reduction from 74.2% (prevalence of benign disease in all 225 patients) to 47.6%. In the experimental arm (88 patients), where the number of false-negative PET is estimated to be ~1.3% (3/225), this number of patients should establish a false-negative rate of maximal 7.5% (actual α error probability of 0.0066 and a power of 0.80). All analyses will be performed according to the intention-to-treat principle, meaning that analysis is based on the initial study-arm allocation and not on the treatment eventually received (e.g. a FDG-PET/CT negative patient in the experimental arm does not refrain from surgery and therefore actually is treated according to the control study arm).

[figure not shown]

Figure 2: Relation between study size (N), study-arm size sizes (n₁ and n₂) and effect size. Empirical relation: N=16.33935*ES^{-1.86986}, R²=.999443). Expected ES=73.1%-40.3%=32.8%

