8.3 Study procedures

8.3.1 FDG-PET/CT of head and neck

A single FDG-PET/CT of the head and neck without a contrast-enhanced CT is performed in all patients in the local centre according to the EANM guidelines [50], independent of allocation results. The scanned area ranges from meatus acusticus externus to the fossa jugularis sternalis (or down to the lower margin of the arcus aortae in case of retrosternal goitre), with arms down and preferably using a head rest (Figure 3, p49). Only a section of the body is scanned as the possibility that a single (PET-positive) lesion outside the thyroid bed is the only evidence of DTC is extremely rare and decreasing the scan range will decrease the effective dose of the investigation. Most of these findings are supposed to be coincidental findings unrelated to DTC and harbour a very low a posterior probability to be of serious consequences. could be considered as "screening a healthy population using FDG-PET" which is highly controversial and probably will lead to increase use of diagnostics and expenditure of public funds and could demotivate physicians in including patients in such a trial. E.g. findings of a positive lesion in the colon would certainly be unrelated to DTC, might lead to endoscopic examination which are costly, could lead to complications for the patient, have a low probability to lead to a serious medical condition requiring therapy and would finally demotivate the physician to include more patients.

[figure not shown]

Figure 3: Position of the normal thyroid.

As an example guideline, in short: patients are asked to refrain from eating and drinking for 6 hours, only water and medications are allowed. In insulin-dependent diabetics, insulin levels should be as low as possible, while maintaining normoglycemia (serum fasting glucose <200 mg/dL [<11.1 mmol/L]). No (short-acting) insulin may be injected in the 4 hours before FDG-infusion to reach normoglycemia.

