8.8 Mid- to long-term follow-up

The duration of short-term follow-up since FDG-PET/CT for this study is set at 12 months, as it is expected that most treatment procedures have taken place within this period and most complications have been resolved. Primary and secondary outcome measures are therefore collected during this one-year period.

In the ideal case that no false-negative FDG-PET/CT-scans occur, it is safe to assume that recurrences and other mid- to long-term sequelae would occur in same fractions in both study arms. However, a one-year follow-up period could be considered too short to conclude a false-negative-fraction for FDG-PET/CT as a delayed diagnosis of malignancy might be made over a year after initial FNAC as DTC usually follows an indolent growth. Also, the costs and utilities (health related quality of life) attributed to delayed treatment would not be completely incorporated in the study most likely leading to an underestimation of false-negative rates, an underestimation of costs, and an overestimation of utility in de experimental study arm due to censoring.

Therefore, five year after the inclusion of the last patient a retrospective study will be conducted using patient files completed with contact with the general practitioners of these patients to investigate the mid- to long-term effects of our intervention.

All treating physicians are aware that about 3.6% of all negative FDG-PET/CT scans are falsenegative (1.3% of all patients included in the study). The short-term follow-up will distinguish a portion of these patients with thyroid malignancy, but probably not all. Therefore, the treating physicians are advised to follow-up the nodules for at least 5 years like "benign nodules" in the ATA-guidelines [6], recommendation 14:

- (a) It is recommended that all benign thyroid nodules be followed with serial US examinations 6–18 months after the initial FNAB. If nodule size is stable (i.e., no more than a 50% change in volume or <20% increase in at least two nodule dimensions in solid nodules or in the solid portion of mixed cystic–solid nodules), the interval before the next follow-up clinical examination or US may be longer, e.g., every 3–5 years.

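### SO2b sets PET-negative patients of arm A against all of arm B, so it selects on PET result in one arm only; the like-for-like comparator is the PET-negative controls

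*Protocol*

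**What the plan says.** Protocol §2.2.2 has two quality-of-life objectives. SO2a compares the arms. SO2b asks whether PET-negative patients of the experimental arm "have a different HRQoL than those who receive surgery independent of the FDG-PET/CT results".

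The comparator phrase matches the protocol's description of the control arm as a whole. §3 has a "control study-arm (arm B: surgery regardless FDG-PET/CT result", and the Summary has "a control study-arm (diagnostic hemithyroidectomy, independent of FDG-PET/CT-result". Nothing in SO2b narrows this to controls with a negative scan. §10.3 gives only general rules for choosing two-group tests, so it does not narrow it either.

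The scan "is performed in all patients in the local centre according to the EANM guidelines", whatever the allocation (§8.3.1). Central readers are blinded to allocation (§3, §8.2.2), results are withheld from patients and treating physicians (§8.3.1), and §11.4 confirms that both PET and histology are obtained in the control arm.

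**The concern.** SO2b appears meant to show what replacing surgery with surveillance after a negative scan does to quality of life. For that, the two groups should differ only in management. Here one group is filtered on PET result and the other is not, so randomisation no longer makes them comparable.

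Two things follow. First, the comparator contains many more patients with cancer. §1.1 says that most malignant nodules lead to a second operation and radio-iodine, and §8.3.3 allows the 3-month questionnaire to be completed directly after surgery and radio-iodine. If cancer diagnosis and treatment lower the scores, surveillance will look better than it is, and any harm from living with an unoperated nodule could be hidden. Second, PET-positive controls would have had surgery in either arm (§5.1), so they carry no information on surveillance versus surgery.

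**Working it through.** **Inputs**
- Pooled meta-analysis, §1.3: "Only 3 out of 83 patients with a negative FDG-PET and 55 out of 142 patients with a positive scan showed a malignancy". Appendix IV gives TP 55, TN 80, FP 87, FN 3, total 225, all nodule sizes.
- §8.8: "about 3.6% of all negative FDG-PET/CT scans are falsenegative".
- Arm sizes, §4.4: "132 patients should be included (88+44 patients in arm A and B respectively".

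**Step 1: reproduce the plan's own count.** PET-negative share = (80 + 3)/225 = 83/225 = 36.9%. In arm A: 88 × 83/225 = 32.5, or 24.6% of 132. This matches the roughly 32 of 132 cancelled operations expected in §3.

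**Step 2: composition of the SO2b groups.**
- Index group (PET-negative, arm A): about 32 patients; cancer 3/83 = 3.6%, or 88 × 3/225 = 1.2 patients.
- Comparator (all of arm B): 44 patients; PET-positive 142/225 = 63.1%, or 44 × 142/225 = 27.8; cancer 58/225 = 25.8%, or 44 × 58/225 = 11.3 patients.
- Ratio of cancer rates: 0.2578/0.0361 = 7.1.

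**Step 3: precision of that ratio.** The exact 95% interval for 3/83 is 0.8% to 10.2%. Holding the overall rate at 25.8%, the ratio ranges from about 2.5 to about 34. The direction is clear; the size is not.

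**Step 4: like-for-like comparator.** PET-negative controls: 44 × 83/225 = 16.2 patients. The expected cancer rate is then 3.6% on both sides, and the expected ratio is 1.

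**Step 5: cost in precision.** In SD units, SE = √(1/n₁ + 1/n₂).
- 32 vs 44: √(1/32 + 1/44) = 0.232
- 32 vs 16: √(1/32 + 1/16) = 0.306
- Ratio: 0.306/0.232 = 1.32

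Detectable difference at two-sided 5% and 80% power (chosen here for illustration) = (1.960 + 0.842) × SE, giving 0.65 SD and 0.86 SD. Both assume no data loss.

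**Step 6: what the case mix could do to the score.** The protocol gives no figure for the quality-of-life difference between cancer and benign patients. Assume 0.2 to 0.8 SD. The shift from case mix alone is d × (0.2578 − 0.0361), which is 0.04 SD at d = 0.2 and 0.18 SD at d = 0.8.

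**The case against.** **Precision.** The best defence is a trade-off. In SD² units the variance is 0.054 for the plan's contrast (1/32 + 1/44) and 0.094 for the matched one (1/32 + 1/16). With the largest bias in Step 6, bias² + variance = 0.18² + 0.054 = 0.086, still below 0.094. Break-even is √(0.094 − 0.054) = 0.20 SD. §1.4.2 also expects quality of life to be reduced only shortly after surgery and to be similar or slightly worse than normal in survivors. So the bias may be modest, and the matched contrast is small. However, the calculation depends on an effect size that the protocol does not give, and it does not justify a non-randomised contrast as the main one when a randomised one is available. It does support keeping the contrast with all of arm B as a description.

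**Existing randomised comparison.** SO2a already compares the arms, and SO2b carries no power claim. This stands and limits the importance of the point.

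**Economics.** A reader might infer that the trial's cost-effectiveness result is biased, because §1.4.3 names the utility of surveillance after a negative scan as the most influential parameter. The document does not support this. §1.4.3 reports the earlier Markov model. The trial's own ICER and iNMB come from the 12-month evaluation alongside the randomised comparison (SO3d, §10.6), and no passage feeds SO2b into them.

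**A perfect fix.** Nor is the matched contrast free of every difference. Only PET-negative patients in arm A learn the decision (§8.2.2), some may still choose surgery (§8.1.2, §8.5), PET status is not a minimisation factor, and about 16 controls leave room for chance imbalance. The unblinding can be seen as part of the strategy under test. The rest are ordinary limits of a small subgroup.

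**Conclusion.** The point holds for SO2b and no further. The objective selects on PET result in one arm only, which gives an expected cancer rate of about 26% in the comparator against about 3.6% in the index group. The sevenfold ratio is a planning expectation based on 3 false negatives, not a trial result. How far it moves the quality-of-life difference cannot be derived from the protocol; 0.04 to 0.18 SD follows only under the assumed range.

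Using PET-negative controls rests on one condition. PET status is obtained after randomisation, so it can serve as a baseline stratum only because scanning does not depend on allocation and reading is blind to it, as §3, §8.2.2 and §8.3.1 provide. §11.2 has the coordinating investigator review the images and also pass on the decision, so it is worth confirming that the reading used for the analysis was the blinded one.

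This is a clear design slip in a secondary objective, cheap to correct. It leaves the primary endpoint, SO2a and the trial's cost-effectiveness analysis untouched.

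**What to change.** Reword SO2b so that its main contrast is PET-negative patients of arm A (about 32) versus PET-negative patients of arm B (about 16). Analyse both as randomised, so that arm A patients who still have surgery stay in arm A. Adjustment for the baseline questionnaire score, already collected under §8.3.3, is preferable. Keep the contrast with all of arm B as descriptive, and state the expected group sizes and limited precision. No change to the economic evaluation is needed.

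The change is one line in the objectives or analysis plan and needs no new data. According to the §4.5 addendum recruitment is complete, so it should be made before questionnaire scores are compared. The cost is a standard error about 32% larger and a detectable difference of about 0.86 SD instead of 0.65 SD.

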2.2.3 Secondary Objective 3: Costs and Cost-Effectiveness

- SO3a: To determine the effect of incorporation of FDG-PET/CT on the mean direct costs (=volume of care multiplied by activity-based costs) per patient during the first 12 months after FDG-PET/CT.
- SO3b: To determine the effect of incorporation of FDG-PET/CT on the average length of hospital stay for treatment of (complications of) thyroid lesions?
- SO3c: To determine the total number of sick leave days for the first three months in the patients (recall, supported by 2 questionnaires)? Do these differ between both study arms?
- SO3d: To determine the incremental Net Monetary Benefit of incorporation of FDG-PET/CT with respect to QALYs (based on EQ-5D-5L index and overall survival) saved including sensitivity analysis.
- SO3e: To determine the incremental Net Monetary Benefit of incorporation of FDG-PET/CT with respect to decrease in unbeneficial treatment. Sensitivity analysis will be performed.
 A mere description will be given as there is no "accepted" value for this kind of analysis.

